7.8.2 Laboratory data

The analyses of laboratory data will be descriptive in nature and will be based on BI standards (6).

The residual effect period of 50 days will be applied to the laboratory data. Laboratory data will be assigned to the treatment period if samples were taken after the first injection of study medication to the date of last administration of study medication plus 50 days. Laboratory data from samples taken on or after the 51st day after the last administration of trial medication will be considered 'Follow-up' data.

Tables and figures in Section 15 of the CTR will include laboratory data from the treatment period; data from the follow-up period will not be included. Listings of laboratory data will display on-treatment and follow-up data, with follow-up data flagged to identify they are from samples taken during the follow-up period.

Possibly clinically significant abnormalities (PCSA) were identified using BI standard rules plus RCTC.

Figures displaying mean and median WBC and neutrophils over time will be provided.

Descriptive statistics for anti-dsDNA, C3 and C4 counts over time will be displayed for all patients in the treated set. For anti-dsDNA, descriptive statistics for patients who are positive at baseline [i.e., >ULN (=75 IU/mL)] will be tabulated and displayed in a figure. For C3 and C4, patients who are below lower limit of normal (LLN) at baseline will be tabulated and displayed in figures. LLN for C3 is 0.9 g/L. LLN for C4 is 0.1 g/L.

Descriptive statistics over time for erythrocytation rate will be provided.

Proprietary confidential information © 2021 Boehringer Ingelheim International GmbH or one or more of its affiliated companies

IgG & IgM values will be listed by treatment, patient and visit. Values outside the normal range will be flagged. Possibly clinically significant abnormalities will be flagged.

7.8.3 Vital signs

Only descriptive statistics are planned for this section of the report.

7.8.4 ECG

No analysis of ECG data is planned. Mean heart rate, PR interval, QRS duration and QT interval will be listed by treatment group by patient.

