2.1.3 Secondary endpoints

- Proportion of patients with CRR at week 52
- Proportion of patients with proteinuria <0.8g/d and without any renal flares at week 52.
- Proportion of patients with CRR at week 52 and sustained steroid reduction to ≤ 5 mg/d from week 26 to week 52.
- Proportion of patients experiencing at least one renal flare during 52 weeks.
- Time to first renal flare over the course of 52 weeks.
- Proportion of patients with confirmed CRR (defined as CRR at both week 42 and week 52 using UP/UC from spot urine)
- Change from baseline in SLEDAI at weeks 12, 26, 42 and 52.

Safety endpoints:

- Physical examination
- Vital signs
- Safety laboratory tests
- Electrocardiogram
- Adverse events (including drug-related AEs)
- Adverse events of special interest (AESI)
- Serious adverse events

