5.2 ASSESSMENT OF SAFETY

Safety will be assessed descriptively based on:

- Physical examination
- Vital signs
- Safety laboratory tests
- Electrocardiogram
- Adverse events (including drug-related AEs)
- Adverse events of special interest (AESI)
- Serious adverse events

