5.2.4 Electrocardiogram

The 12-lead ECGs will be recorded according to local standard procedures at the visits indicated in the [Flow Charts](#). Automatically generated interval data (PR, QRS, QT) and heart rate on the printed ECG will be collected on the eCRF. QTcB and QTcF will be calculated with HR and QT interval.

Rate, rhythm and repolarisation changes have to be evaluated, compared to previous charts, and assessed for clinical relevance. Clinically relevant abnormal findings will be reported either as baseline conditions (if identified at the screening visit) or otherwise as adverse events and will be followed up and/or treated as medically appropriate. If necessary, additional ECGs may be repeated for quality or safety reasons and the repeated ECG will be used for analysis.

Dated and signed printouts of ECG with findings should be documented in patient's medical record.

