7.3.4 Safety analyses

Adverse events will be coded using the Medical Dictionary for Drug Regulatory Activities (MedDRA). Standard BI summary tables and listings will be produced. All adverse events with an onset between start of treatment and end of the residual effect period (REP), a period of 50 days after the last dose of trial medication, will be assigned to the on-treatment period for evaluation. Analysis will be performed based on randomised treatment.

All treated patients will be included in the safety analysis. In general, safety analyses will be descriptive in nature and based on BI standards. No hypothesis testing is planned. Statistical analysis and reporting of adverse events will concentrate on treatment-emergent adverse events, i.e. all adverse events occurring between start of treatment and end of the REP. Adverse events that start before first drug intake and deteriorate under treatment will also be considered as 'treatment-emergent'.

Frequency, severity and causal relationship of adverse events will be tabulated by system organ class and preferred term after coding according to the current version of the MedDRA at the database lock.

AESIs will be summarized separately using a standard BI summary table. Note that there is one SAE definition specified in [Section 5.2.5.1](#) for Japan only. Laboratory data will be analysed both quantitatively as well as qualitatively. The latter will be done via comparison of laboratory data to their reference ranges. Values outside the reference range as well as values defined as clinically relevant will be summarised. Treatment groups will be compared descriptively with regard to distribution parameters as well as with regard to frequency and percentage of patients with abnormal values or clinically relevant abnormal values.

Vital signs, physical examinations, or other safety-relevant data observed at screening, baseline, during the course of the trial and at the end-of-trial evaluation will be assessed with regard to possible changes compared to findings before start of treatment.

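### SAP 7.8.4 omits the QTcB and QTcF values and the descriptive ECG summary that the protocol provides for

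*SAP*

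**What the plan says.** **Protocol.** Section 2.1.3 has "Electrocardiogram" in its list of safety endpoints. Section 5.2 opens with "Safety will be assessed descriptively based on" and the list that follows again includes the ECG. Section 5.2.4 sets out the data: "Automatically generated interval data (PR, QRS, QT) and heart rate on the printed ECG will be collected on the eCRF", and then "QTcB and QTcF will be calculated with HR and QT interval". Flow Chart 1 schedules a 12-lead ECG at baseline and at weeks 12, 26 and 52. Section 7.3.4 says that vital signs, physical examinations and other safety-relevant data "will be assessed with regard to possible changes compared to findings before start of treatment"; it does not name the ECG in that sentence.

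**SAP.** Section 7.8 gives the general rule for safety data: frequencies for categorical variables, descriptive statistics for continuous ones. Section 7.8.3 keeps descriptive statistics for vital signs. Section 7.8.4, on ECG, reads: "No analysis of ECG data is planned. Mean heart rate, PR interval, QRS duration and QT interval will be listed", by treatment group and patient. QTcB and QTcF do not appear. The readable part of section 4, which records changes to the planned analysis, does not refer to ECG.

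**The concern.** The protocol promises two things for ECG: corrected QT values and a descriptive assessment. The SAP provides neither. It sets aside the protocol's derivation and its own general rule for continuous safety data, and gives no reason in the text that can be read.

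The corrected values matter because QT shortens as heart rate rises. Raw QT values from patients or visits with different heart rates are therefore not directly comparable. The summary matters because this is a dose-ranging trial with a placebo arm. A modest shift in an interval that increases with dose would be seen by comparing arms over visits. It is hard to see in a patient-by-patient listing, and it need not produce any single value that an investigator calls clinically relevant.

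**Working it through.** No figure in the documents has to be reproduced. The check compares the texts and adds one illustration.

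**Comparison of the texts**

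| Item | Protocol | SAP |
|---|---|---|
| Status of ECG | Safety endpoint (2.1.3) | No analysis planned (7.8.4) |
| Type of assessment | Descriptive (5.2) | By-patient listing only (7.8.4), although 7.8 tabulates continuous safety data |
| Heart rate, PR, QRS, QT | Collected on the eCRF (5.2.4) | Listed (7.8.4) |
| QTcB, QTcF | To be calculated (5.2.4) | Not mentioned |
| Change from before treatment | Safety-relevant data in general (7.3.4) | Not planned for ECG |
| Notice of a change | – | None in the readable text of section 4 |

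The firm mismatches are the corrected QT and the descriptive assessment. The change-from-baseline row is weaker support, because 7.3.4 reaches ECG only through its general wording.

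**Why uncorrected QT is not enough on its own.** With RR = 60/HR in seconds, QTcF = QT/RR^(1/3) and QTcB = QT/RR^(1/2). The documents give no QT or heart-rate values, so the inputs are assumptions: QT of 380 and 400 ms, heart rate of 60 to 90 bpm.

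Worked example at 90 bpm with QT 400 ms: RR = 60/90 = 0.667. Then QTcF = 400/0.667^(1/3) = 457.9 ms and QTcB = 400/0.667^(1/2) = 489.9 ms.

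| Heart rate (bpm) | QTcF, QT 380 | QTcB, QT 380 | QTcF, QT 400 | QTcB, QT 400 |
|---|---|---|---|---|
| 60 | 380.0 | 380.0 | 400.0 | 400.0 |
| 70 | 400.0 | 410.4 | 421.1 | 432.0 |
| 80 | 418.2 | 438.8 | 440.3 | 461.9 |
| 90 | 435.0 | 465.4 | 457.9 | 489.9 |

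From 60 to 90 bpm an unchanged QT therefore corresponds to a QTcF span of 435.0 − 380.0 = 55.0 ms (QT 380) or 457.9 − 400.0 = 57.9 ms (QT 400). For QTcB the spans are 85.4 and 89.9 ms. The size depends on the heart-rate range chosen; a wider range gives a wider span.

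**Amount of data.** The protocol expects about 60 patients over four arms, which is 60/4 = 15 per arm if they were evenly spread (SAP 7.4.1 says they are not). Each has up to four scheduled ECGs in this trial.

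**The case against.** The case for leaving the SAP as it is has several parts.

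- **ECG safety is not unreported.** Protocol 5.2.4 says "Rate, rhythm and repolarisation changes have to be evaluated, compared to previous charts, and assessed for clinical relevance", and "Clinically relevant abnormal findings will be reported either as baseline conditions (if identified at the screening visit) or otherwise as adverse events". Section 5.2.5.2 repeats that clinically relevant ECG changes are recorded as adverse events, and SAP 7.8.1 tabulates adverse events by treatment, system organ class and preferred term. This stands. A reader might infer that the ECGs would lead to no safety statement at all, and the documents do not support that. The route does, however, depend on case-by-case judgement by investigators, so it does not replace a descriptive summary.
- **QTc can be recovered.** Heart rate is listed beside QT, and those are the two inputs the protocol names for QTc. This stands too. It would be wrong to say that the listing cannot show a repolarisation change; that is true only of QT read without its heart rate. But the protocol says the corrected values will be calculated, and the SAP leaves that to the reader.
- **The protocol prescribes no table.** Section 5.2.4 asks for QTc to be calculated, not for any particular layout, and the sponsor's reporting standards cited in the SAP are not available here. That is fair for the format. It does not remove the descriptive assessment in 5.2 or the SAP's own rule in 7.8.
- **The trial is small and exploratory.** ECGs follow local procedures with machine-read intervals, and summaries over four small arms will be sparse. This limits the value of the tables. Descriptive statistics are nevertheless all that the protocol asks for.

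**Conclusion.** The mismatch holds on the current text of both documents. SAP 7.8.4 leaves out a derivation that the protocol specifies and the descriptive assessment that goes with it, and it departs from SAP 7.8. The consequence is minor: the report would lack the promised QTc values and any view by arm of a dose-related ECG shift. No efficacy result is affected.

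Two further inferences should be avoided. It cannot be said that the change is undisclosed, because part of SAP section 4 is blacked out; only the readable text is silent. Nor can it be said that two years of ECG data go unused. The documents show the ECG schedule of this trial only, and how ECGs were recorded and reported in 1293.10 is not visible beyond the end-of-treatment visit that serves as baseline here.

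The conclusion rests on the texts alone. The QTc figures are an illustration under assumed QT and heart-rate values and say nothing about what this drug does.

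**What to change.** In SAP 7.8.4:

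1. Derive QTcB and QTcF from the recorded QT and heart rate and add both to the listing.
2. Replace the statement that no analysis is planned with a descriptive summary of heart rate, PR, QRS and QTc by arm and visit, with change from baseline. Use the sponsor's standard outlier categories if there are any.
3. State which baseline applies. SAP 6.7 defaults to the start of 1293.10, whereas the Visit 1 ECG of this trial is the 1293.10 end-of-treatment recording.

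If the sponsor prefers to keep a listing only, QTcB and QTcF should still be in it, and section 4 should record and justify dropping the summary.

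The cost is a little extra programming on data already collected. With about 60 patients over four arms the summaries will be sparse and should be read as descriptive only.

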7.8.5 Others

Not applicable.

[figure not shown]
8. TIMEPOINT OF RELEASE OF TREATMENT INFORMATION

Once the last patient has completed their End-of-Treatment (EOT) visit and all corresponding data has been entered and cleaned to the level documented in the “Data Delivery Request” (DDR) form, the data will be declared ready to be unblinded via the “Data Ready to be Unblinded and/or Final Trial Closure Notification” (RUN) form. Then the treatment information will be released for analysis.

[figure not shown]
The data collection for the off-treatment residual effect period until the End-of-Study (EoS)/ Follow-Up visit will continue into the unblinded trial database. Once trial data collection has been completed and all data has been entered and cleaned as documented on the RUN form, a final data lock will be performed.

Proprietary confidential information © 2021 Boehringer Ingelheim International GmbH or one or more of its affiliated companies

11. HISTORY TABLE

This is a revised TSAP including the following modifications to the final TSAP

Table 11: 1 History table

Version	Date (DD-MMM-YY)	Author	Sections changed	Brief description of change
1	14-DEC-17		None	This is the final TSAP
2	17-JUN-21		All	This is a revised TSAP updated to reflect issues identified during data review, learnings from project team & KOLs and specifications to execute the statistical analysis. Updates based on CTP Amendment #2 are also included.
